13.1 Sample Size Determination

The sample sizes of 20 subjects for the training set and 30 subjects for the validation set were determined by simulation studies (see Appendix A). The goal of these studies was to select sample sizes with a high probability of representation in as many of the subgroups of interest as possible. These sample sizes provide a $> 90\%$ chance of representation for underlying conditions of interest and Fitzpatrick skin type groups. In addition, these sample sizes reliably provide variability across age groups, genders and lesion locations.

If areas are assumed to be independent, the sample size of at least 360 areas in the validation set will produce confidence intervals with a width of $\pm 6.2\%$. The areas are correlated, which decreases precision, but the number of areas is expected to be larger, which increases it. If these factors offset, a confidence interval width of $\pm 6.2\%$ is a reasonable estimate of the expected results.

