11.3 Image Analysis Stage

The Image Analysis stage includes the following three phases:

1. Development of consensus training materials by three (3) Comparative Readers
2. Validation of Enspectra Health Images with Ground Truth Pathology by three (3) Comparative Readers
3. Performance testing (Blinded Reader assessment of Enspectra Health images)

11.3.1 *Phase 1: Training/Consensus*

1. Three Comparative Readers (CRs) will train as a group using the [REDACTED] VIO images and all available pathology slides. Comparative readers will assess a minimum of [REDACTED] [REDACTED]. VIO images from 20 lesions on 20 subjects meeting the requirements described above in Tables 1-5 will be evaluated for this training assessment.
2. CRs will label the images [REDACTED]
[REDACTED]
[REDACTED]
[REDACTED]
[REDACTED]
3. Images will be marked as elements are identified but exhaustive annotation is not required. Samples will be reviewed until complete consensus achieved. Secondary histopathology characteristics will also be evaluated and recorded.
4. The output of this phase of the study will be a set of 20 training samples consisting of matched VIO images and ground truth pathology slides.

11.3.2 *Phase 2: Validation* (VIO Image Assessment in Comparison with Ground Truth Pathology) and Establishment of an “Answer Key”

1. A total of 30 VIO images from 30 subjects meeting the requirements described above in Tables 1-5 will be evaluated in this validation assessment.
2. Two experienced physicians with dermatopathology expertise will serve as the primary CRs. A third expert CR, with RCM experience, will adjudicate discrepancies between the two primary CRs.
3. Two primary CRs will assess the [REDACTED] VIO images and predict histology.
[REDACTED]
[REDACTED]
4. The expert CR will review all pairs and will work with the two primary CRs until complete consensus achieved (i.e., until 100% VIO image v. ground truth pathology achieved across all 3 CRs). Achieving 100% agreement/consensus at the completion of this process represents success for Primary Endpoint 1: 100% agreement and validation of specific tissue features on VIO images (epidermis, dermis, collagen, blood vessels and pigment) in comparison to gold standard pathology images in Comparative Reader assessment.

5. The output of this validation process will establish the answer key for the performance testing assessment.

11.3.3 *Phase 3: Performance Testing* (VIO Image Assessment by Readers Blinded to Pathology Results)

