13.2.4 Performance Testing of Blinded Readers

Once the answer key is finalized for the validation set, 3 blinded readers will be used for performance testing. The blinded readers will be trained using the training set, and will then be provided with the VIO images only from the validation set. Each blinded reader will classify the primary histopathology features and regions for each of the approximately 360 areas in the validation set and identify secondary histopathology characteristics in each VIO image.

Accuracy will be assessed for primary histopathology characteristics only, compared to the answer key, as the proportion of total points for each of the blinded reviewers as described in section 11.5.

The accuracy assessment will be performed using a conditional, generalized linear mixed model (GLMM) to account for correlation among multiple images obtained for the same subject, and for correlation of responses within each reviewer. Once each response has been scored, the data will be condensed to 1 record per patient per reviewer. The dependent variable will be the number of points obtained divided by the maximum number of points possible. The GLMM will use a binomial response distribution and a logit link function. A compound symmetry variance-covariance matrix will be used to account for correlation. Random effects will be included for each subject-reviewer cluster. Reviewer will be included as a model covariate, and the correlation-adjusted proportion correct will be calculated separately for each reviewer by applying the standard logistic function to the least-square means by reviewer. This GLMM framework (with an intercept term) will be used to produce overall and reviewer-specific point estimates and 95% confidence intervals. The point-estimate target for overall accuracy is 90%.

Inter-rater agreement among the BRs will be assessed using Kappa statistics, and the target for agreement is 90%. Overall accuracy compared to the answer key across the subgroups will be assessed by adding each subgroup to the GLMM as a categorical variable. Accuracy for secondary histopathology characteristics may also be reported, but there are no *a priori* targets.

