1.1.1.2 Minimize bias in assignment, and

1.1.1.3 Meet minimum enrollment targets for both the Training and Validation sets as specified in the study protocol.

1.1.2 To assign samples, 500 randomization assignment schedules will be generated. The first schedule that simultaneously meets the minimum enrollment targets for both the Training set and Validation set, and meets the requirement of a maximum Standard Mean Difference (SMD) <0.2 will be selected and used to assign samples to these sets.

¹ Austin PC. Balance diagnostics for comparing the distribution of baseline covariates between treatment groups in propensity-score matched samples. *Stat Med*. 2009;28(25):3083-3107. doi:10.1002/sim.3697

² Cohen J. *Statistical Power Analysis for the Behavioral Sciences* (2nd edn). Lawrence Erlbaum Associates Publishers: Hillsdale, NJ, 1988.

meeting pre-specified requirements. This schedule will be used to assign

The study protocol requires a minimum enrollment of (50) subjects, and assignment of 20 subjects to the Training Set and 30 subjects to the Validation Set. If more than 50 subjects are enrolled, excess subjects will be assigned to maintain the original ratio (40% of subjects assigned to the Training Set, 60% of subjects assigned to the Validation Set).

1.2.10 Validation of the Assignment Spreadsheet.

1.2.10.1 Prior to usage with real study data, the Assignment Spreadsheet will be tested and validated with simulated data. To generate a simulated data set, randomized categories will be assigned to hypothetical subjects using the probabilities expected in the population (Tables 1-5).

[REDACTED]

[REDACTED]

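### Section 13.1 gives ±6.2% for 360 independent areas, but 6.2% is the full 95% interval width at 90% accuracy (half-width ±3.1%), and carrying it over to correlated areas is unsupported

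*Combined protocol and SAP*

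**What the plan says.** The second paragraph of section 13.1 states that, with independent areas, "the sample size of at least 360 areas in the validation set will produce confidence intervals with a width of" ±6.2%. It then concedes dependence: "The areas are correlated, which decreases precision, but the number of areas is expected to be larger, which increases it". It closes with a conditional, "If these factors offset, a confidence interval width of" ±6.2%, which it calls a reasonable expectation. The paragraph names no accuracy, confidence level, ICC, design effect or expected number of areas above 360.

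Section 13.2.4 supplies the likely inputs. Each blinded reader classifies "approximately 360 areas in the validation set". The mixed model yields "overall and reviewer-specific point estimates and 95% confidence intervals". On the target, it says: "The point-estimate target for overall accuracy is 90" per cent.

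The number of clusters comes from two places. Section 11.3.2 takes "A total of 30 VIO images from 30 subjects" into validation. Appendix C says that, if more than 50 subjects are enrolled, "excess subjects will be assigned to maintain the original ratio" (40% training, 60% validation). With the maximum enrolment of 65, that gives 0.6 × 65 = 39 validation subjects.

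**The concern.** A ± sign denotes a half-width, yet 6.2 points is what 360 independent areas give as a full width at 90% accuracy. A reader cannot tell which is meant, and the two readings differ by a factor of two.

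The paragraph then transfers the same number to correlated areas by supposing that two unquantified effects cancel. With a fixed number of subjects, adding areas within subjects has a ceiling, so cancellation cannot be taken for granted.

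This is the only precision figure the plan gives for blinded-reader accuracy, the basis of the second primary endpoint. Because that endpoint is judged on a point estimate, the interval is what tells a reader how firmly the result supports accuracy near 90%.

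**Working it through.** **Inputs.** n = 360 areas (13.1). Accuracy p = 0.90 and 95% two-sided confidence (13.2.4; 13.1 states neither). N = 30 validation subjects (11.3.2, 13.1), so m = 360/30 = 12 areas per subject; N = 39 at maximum enrolment (Appendix C). The ICC is not in the documents, so values of 0.1 to 0.3 are assumed. Each area is taken as scored correct or incorrect.

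**1. The plan's figure under independence.**

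- Half-width = 1.96 × √(0.9 × 0.1/360) = 0.0310, so ±3.1%; full width 6.20%.
- Full width by other methods at 324/360: Wilson 6.2, logit 6.25, exact 6.5 points.
- The half-width is largest at p = 0.5: 1.96 × √(0.25/360) = 0.0516, so ±5.2% (exact ±5.3%). At 95% confidence ±6.2% is therefore out of reach for any accuracy.
- A half-width of 6.2 points needs (1.96/0.062)² × 0.09 ≈ 90 independent areas at p = 0.9, or about 250 at p = 0.5.

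The match to 6.20 as a full width is exact.

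**2. Half-width with clustering, single reader.** The effective sample size is n_eff = N·m / (1 + (m − 1)·ICC), and the half-width is 1.96 × √(0.09/n_eff). With m = 12:

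| ICC | N = 30: n_eff | half-width | N = 39: n_eff | half-width |
|---|---|---|---|---|
| 0 | 360 | ±3.1% | 468 | ±2.7% |
| 0.1 | 171 | ±4.5% | 223 | ±3.9% |
| 0.2 | 113 | ±5.5% | 146 | ±4.9% |
| 0.3 | 84 | ±6.4% | 109 | ±5.6% |

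A half-width of ±6.2% needs n_eff = 90. That is a design effect of 360/90 = 4.0, or ICC 3.0/11 = 0.27, with 30 subjects; and 468/90 = 5.2, or ICC 4.2/11 = 0.38, with 39.

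**3. Can more areas offset the correlation?** As m grows, n_eff approaches N/ICC and cannot exceed it. An effective 360 is unattainable from ICC = 30/360 = 0.083 (30 subjects) or 39/360 = 0.108 (39 subjects). Below that, m = 360(1 − ICC)/(N − 360·ICC). For N = 30:

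| ICC | areas per subject | total areas |
|---|---|---|
| 0.01 | 13.5 | 405 |
| 0.02 | 15.5 | 464 |
| 0.03 | 18.2 | 546 |
| 0.05 | 28.5 | 855 |
| 0.08 | 276 | 8,280 |

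With 39 subjects at 12 areas each, 468/(1 + 11·ICC) = 360 gives ICC = 0.027 as the limit.

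**4. Overall accuracy over three similar readers.** Multiply the single-reader half-width by √((1 + 2r)/3), where r is the correlation of reader errors, from 0 to 1. With 30 subjects this gives ±2.6 to 4.5% (ICC 0.1), ±3.2 to 5.5% (0.2) and ±3.7 to 6.4% (0.3). Treating three readers as 1,080 independent readings would give ±1.8%, which does not match the plan either.

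**The case against.** **The inputs are inferred.** Section 13.1 names neither 90% nor 95%, and section 13.2.4 also plans Kappa statistics. With 90% observed agreement and 50% chance agreement, a simple large-sample half-width for Kappa is 3.10/0.5 = ±6.2%. It is fair to say that the diagnosis rests on inputs from 13.2.4. The Kappa reading, however, needs a chance agreement that appears nowhere in the plan, and it moves to 3.10/0.6 = ±5.2% at 40%. The accuracy reading needs only the plan's own figures.

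**Scoring details are not visible.** Sections 13.2.3 and 13.2.4 refer to sections 11.4 and 11.5, which are not in the public text, and accuracy is a share of points. The figures here therefore assume equally weighted areas scored right or wrong. Under that assumption no undisclosed area count makes ±6.2% a half-width for 360 independent areas, and 13.1 says at least 360, so more would only narrow it.

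**360 is a floor.** Section 12.6 expects about 4 to 8 selected images per site, and 13.3 requires at least 4. If the area count doubled to 24 per subject, half-widths with 30 subjects at ICC 0.1, 0.2 and 0.3 would be ±4.0%, ±5.2% and ±6.2%. The offset would hold to ICC (720/360 − 1)/23 = 0.043 with 30 subjects and (936/360 − 1)/23 = 0.070 with 39. This is a fair extension, but it moves the half-widths only slightly, and 13.2.4 still plans on approximately 360 areas.

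**The plan is candid and nothing turns on the figure.** Section 13.1 admits the correlation and words the offset conditionally, the mixed model allows for it, and the ± error understates precision under independence. All true. These points limit the consequence but do not make the sentence correct.

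**Conclusion.** The concern holds. Under 13.1's own independence assumption, with the 90% target and 95% level of 13.2.4, the half-width is ±3.1%; the stated ±6.2% is the full width carrying a ± sign, a factor of two. Even without assuming 90%, ±6.2% exceeds the largest possible 95% half-width of ±5.2%.

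The carry-over to correlated areas is possible only at small ICCs and has no stated support. Read as a half-width, ±6.2% would be right by coincidence, near ICC 0.27 with 30 subjects or 0.38 with 39, at 12 areas each. Read as a full width, it is optimistic for a single reader at any positive ICC with 360 areas from 30 subjects.

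The clustered figures rest on assumed ICCs and a design-effect approximation rather than the planned logit mixed model, so they show the order of size only.

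The consequence is limited to the stated precision. The sample size came from the representation simulations in Appendix A, and the accuracy target is a point estimate, so no enrolment or success decision changes.

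**What to change.** Replace the second paragraph of section 13.1, including its offset sentence, with text such as:

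> At 90% accuracy, 360 independent areas give a 95% CI of ±3.1% (full width 6.2%). Allowing for clustering, with about 12 areas in each of 30 subjects and assumed (not estimated) ICCs of 0.1, 0.2 and 0.3, the expected half-width for a single reader is about ±4.5%, ±5.5% and ±6.4% (±3.9%, ±4.9% and ±5.6% with 39 subjects). The interval for overall accuracy across three readers of similar accuracy will be no wider, and narrower unless reader errors are fully correlated.

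If the sponsor expects clearly more than 12 areas per subject, the paragraph should state that number and recompute the range from it.

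The cost is SAP wording only, with no change to enrolment, analysis or success rule. The drawback is that one number becomes a range that depends on an assumed ICC. With 30 subjects that range looks better than the present ±6.2% below an ICC of about 0.27 and worse above it.

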13.2 Statistical Analysis Methods

13.2.1 General Definitions

Subgroups of Interest

This study aims to recruit subjects and lesions across a range of demographic and clinical subgroups. The sample size was selected so that there was high probability of representation across the categories seen in clinical practice. Specifically, the subgroups of interest are:

- Underlying skin condition (BCC, SCC, other)
- Fitzpatrick skin type (I, II, III, IV-VI)
- Lesion location (head and neck, limb, torso)
- Age group (18 to 49, 50 to 64 and 65+)
- Sex (men, women)

13.2.2 Analysis of Training Set

Descriptive statistics only will be produced for the entire training set of VIO images and full histopathology slides. The purpose of this summary is to describe the training sample data set, and to verify that the training set is similar to the validation set. As such, the number of patients, average number of lesions within subject, and average number of photos within subject will be summarized using n, mean, standard deviation and range. In addition, the distribution of lesions across relevant subgroups will be tabulated (see section 11.2). The distribution of primary histopathology characteristics observed in the training set will also be tabulated. The incidence of secondary histopathology characteristics observed in the training set will also be summarized.

. Since this phase will continue until complete consensus is achieved for these images, no analysis of this process will be performed.

Other materials may be used to train Blinded Readers at the CRs' discretion, including but not limited to third party publications, data from VIO prototype devices, and VIO images from uninvolved skin sites. No Validation Set data may be used for training.

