1. Three Blinded Readers (BR) will be trained using the training set developed in Phase 1. Training materials may also be supplemented with other data sets [REDACTED]
[REDACTED]
2. The Phase 2 Validation Set and the answer key derived from such will be used for the BR assessment. BRs will assess [REDACTED]
Assessment of performance of the BRs defines the success of Primary Endpoint 2: >90% agreement between Blinded Reader VIO image assessment and answer key developed from validation assessment.

12 Study Procedures

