13.2.3 Comparison of Validation Set to Ground Truth Histology

First, an expert reviewer and 2 comparative reviewers will assess each of the VIO images, blinded to the histopathology results. For each area, the reviewer will classify the predicted primary histopathology characteristics according to the categories described in section 11.4. Second, the expert reviewer will determine the actual primary histopathology characteristics based on the histopathology results. Third, the predicted characteristics will be compared to the expert reviewer classification.

An iterative review process will be performed until there is complete consensus across all reviewers. The output of this iterative review process will be an “answer key” that reflects 100% consensus of the comparative results from the VIO image and pathology across all 3 comparative readers. Achieving 100% agreement/concensus through this process satisfies the first Primary Endpoint.

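### The comparative readers who agree the answer key may choose extra blinded-reader training material, and the visible text does not say that this choice is made before they know the key

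*Combined protocol and SAP*

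**What the plan says.** **Who does what.** Section 11.3 gives Phase 1 to the CRs ("Development of consensus training materials by three (3) Comparative Readers") and Phase 2 to the same role ("Validation of Enspectra Health Images with Ground Truth Pathology by three (3) Comparative Readers"). No second panel is described.

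**What Phase 2 produces.** Section 11.3.2 states: "The output of this validation process will establish the answer key for the performance testing assessment". Section 13.2.3 adds that the key "reflects 100% consensus of the comparative results from the VIO image and pathology across all 3 comparative readers".

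**When the blinded readers (BRs) come in.** Section 13.2.4: "Once the answer key is finalized for the validation set, 3 blinded readers will be used for performance testing". Training them is item 1 of Phase 3 in Section 11.3.3.

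**What they may be trained on.** Section 11.3.3 starts from the Phase 1 training set and continues: "Training materials may also be supplemented with other data sets". The text that follows is redacted. Section 13.2.2 says: "Other materials may be used to train Blinded Readers at the CRs' discretion". Its list of examples is open-ended: outside publications, prototype-device data and images of uninvolved skin. The limit comes next: "No Validation Set data may be used for training". Section 13.2.4 names only the training set as BR training.

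**The concern.** Primary Endpoint 2 is meant to show how well readers perform on images they have not been prepared for. To agree every item of the key, the CRs must work through the validation images and resolve their disagreements, so they learn which areas are hard. If the same people then choose extra teaching material, the teaching can lean toward those areas without a single validation image being shown. No bad intent is needed; an experienced teacher naturally stresses what proved difficult.

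Accuracy against the key could then overstate what readers would achieve with a package chosen without that knowledge, and the distortion would favour success. Section 13.2.4 judges overall accuracy by a point estimate against 90%, so no confidence bound absorbs a modest upward shift.

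**Working it through.** The plan gives no figure for this point, so the check is mainly a reading of the sections in sequence.

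1. **Do the people with discretion know the key?** Yes. Section 13.2.2 gives the discretion to the CRs, and under 13.2.3 all three CRs agree the key.

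2. **Can the choice follow the key?** It is permitted but not stated. Section 11.3.3 places BR training, with its permission to supplement, after Phase 2, and 13.2.4 uses the BRs once the key is final. Against that, Section 9 calls stage 1 the development of training materials, and 13.2.2 precedes the validation section. No visible sentence dates the choice.

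3. **What does the stated bar cover?** It covers Validation Set data. It does not cover a CR's knowledge of those data, so a CR can comply fully and still select look-alike images from another source.

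4. **Is the bar's scope clear?** Not entirely. Section 12.6 has 2-10 images taken at each subject's uninvolved site, and 13.2.2 allows uninvolved-site images for training. No visible text says whether those from validation subjects count as Validation Set data.

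5. **Does another control reach the supplements?** None is visible. Appendix C pre-specifies assignment of study samples to the two sets, with a maximum standardized difference below 0.2. Section 13.2.2 plans a description of the training set. Neither covers supplementary material. The training records in Section 6.2 concern device users.

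6. **Do the sections agree?** No. Sections 11.3.3 and 13.2.2 allow supplements; 13.2.4 mentions only the training set.

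**Sensitivity of the success rule (illustration only).** This shows how strongly a point-estimate rule reacts near its threshold. It does not estimate the bias.

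- From the plan: about 360 areas (13.2.4), 30 validation subjects (13.1), 3 BRs and the 90% target (13.2.4).
- Assumed: areas split evenly, 360 / 30 = 12 per subject; each area scored right or wrong; success if pooled accuracy exceeds 90%; true accuracy varying between subjects by a beta distribution with intraclass correlation (ICC) 0 to 0.20, shared by the three readers.
- Readings per subject: 12 × 3 = 36. Total: 36 × 30 = 1,080. Each cell rests on 20,000 simulated studies.

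| ICC | Chance of passing, true accuracy 88% | Chance of passing, true accuracy 90% | Difference (points) |
|---|---|---|---|
| 0 | 1.7% | 49.3% | 47.6 |
| 0.05 | 10.3% | 50.9% | 40.6 |
| 0.10 | 16.3% | 51.2% | 34.9 |
| 0.20 | 23.7% | 51.0% | 27.3 |

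Under these assumptions, a shift of two points just below the threshold would raise the chance of passing by about 27 to 48 percentage points. The documents do not say whether supplementary training could cause a shift of that size, or any shift.

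**The case against.** The strongest reply is that the plan already blocks the serious route. Validation Set data may not be used for training, and Sections 3 and 9 keep training samples out of validation and performance testing. The features to be recognised (epidermis, dermis, collagen, blood vessels, pigment) are generic, so a publication or prototype image may add little. Similarity between the training and validation sets is itself an intended design feature. Timing is not fixed as late, and the redacted text in 11.3.3 may contain a limit on source, date or approval.

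Most of this stands and sets the limits of the point:

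- A reader might infer that the plan has the CRs choose material after seeing the answers. The documents allow this but do not say it.
- A reader might infer that validation images can reach the BRs. The bar in 13.2.2 forbids it; the only doubtful case is uninvolved-site images from validation subjects.
- A reader might conclude that supplementation is unrestricted. With text redacted straight after the permission in 11.3.3, that cannot be claimed.
- A reader might convert two percentage points into 0.02 × 360 = 7.2 areas per reader and treat that as the size of the problem. It is only the distance between two chosen percentages. Moreover, 13.2.4 scores points out of a maximum for each subject and reader, and sets its target for overall accuracy.

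The reply does not remove the core. The intended similarity of the sets comes from an assignment procedure fixed in advance, whereas supplements are left to people who will know, or already know, the key.

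**Conclusion.** The point holds as a statement of what the visible plan permits. It goes beyond a missing detail, because the plan expressly gives the holders of the key a choice that can affect Primary Endpoint 2. The bar on Validation Set data closes direct leakage but leaves open selection or emphasis informed by the key. The possible bias runs toward success. Its size cannot be estimated from the documents, and it may be nil if the material is in fact chosen before Phase 2. That training would be tuned to the test set is not shown; the supportable statement is that it could be.

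The conclusion assumes that the CRs named in 13.2.2 are those who agree the key, as the shared role indicates, and that the redacted text in 11.3.3 sets no limit on timing or chooser. If it does, only the scope of the bar and the mismatch with 13.2.4 remain. This is a worthwhile, inexpensive improvement rather than a flaw that invalidates the endpoint.

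**What to change.** - In 11.3.3 and 13.2.2, state that the full BR training package, including all supplementary material, is fixed and version-logged before any CR opens the validation images.
- State that any later addition is documented, with its date and reason, and is chosen or approved by someone who has seen neither the validation set nor the key.
- In 13.2.2, state that uninvolved-site images from validation subjects count as Validation Set data and are therefore barred from training.
- Align 13.2.4 with 11.3.3 and 13.2.2, so that all three describe the same training package.
- If the redacted text already sets such a limit, repeat it in 13.2.2.

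The cost is a few sentences, a version log and an earlier date for assembling the package. No extra subjects, readers or images are needed. The drawback is less freedom to add training material late; the documented route for later additions keeps some of it.
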